#### 3.8.6 Multiple assessments within visit windows

For visit windows defined in Visit windows Section 3.8.3.2, multiple records may exist in one particular visit window. The following rules (unless otherwise specified) will be applied to obtain one value per subject per visit window which will be used in the by-visit summaries.

- For quantitative variables (i.e., continuous variables for which summary statistics and change from baseline tables will be provided), the average of the multiple records will be used.
- For qualitative variables (i.e., binary or nominal variables for which incidence rates and frequency distribution tables will be provided), the worst record will be used. It is noted that in the analyses performed, worst case is always well defined.

Note that "Last assessment on study drug" is not like other visit windows but more like a single time point. The assessment to be summarized at that time point is the last on drug observation which is the last observation a subject has while he or she is on study drug. Therefore, the above multiple assessment rules do not apply.

In addition, the multiple assessment rules do not apply to the first dose/second dose monitoring data and the restart dose monitoring data.

For tables to display worst case scenario, such as shift tables, and on listings, multiple assessments will be used as they are and no average values will be taken.

#### 3.8.7 Last dose day of randomized study medication

The last dose date of the randomized study drug will be collected on three CRFs:

- 1) The last date subject took study drug on the study completion CRF (CMP panel),
- 2) The last date subject took study drug on the study drug discontinuation CRF (CMP panel),
- 3) The last end date on the study drug administration record CRF (DAR panel).

The last dose date recorded in the CMP panel will be used. If the last dose date in the CMP panel is partial date, impute the first day for missing day and January for missing month. If the last dose date in the CMP panel is completely missing, the last dose date recorded on the DAR panel will be used.

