#### 3.6 Study medication

Duration of exposure to randomized study medication will be summarized on the safety set by presenting the number (and percentage) of subjects being exposed for a minimum duration of time as specified in Table 1-3 Duration in terms of number of days as shown in the second column will be used in the summary for the display of duration.

Duration of exposure is the number of days on study drug during the core study phase. The days when the subject does not take the study drug will be excluded. That is, duration of exposure will exclude periods of temporary interruption of study medication. Note: for the last dosing interval entered on the Dosage Administration Record CRF, if the dosing end date is partial date, impute the first day for missing day and January for missing month.

Summary statistics of duration of exposure to study medication will also be presented, which included mean, SD, minimum, maximum, etc.

For each treatment group, the patient-years, which will be calculated as (the sum of the number of days on study drug for all subjects in the group)/365.25, will also be presented.

Table 1-3 Definitions of time-intervals used to summarize exposure to study medication

Duration	Duration in terms of number of days
Any Exposure	≥1 day
≥1 week	≥7 days
≥2 weeks	≥14 days
≥1 month	≥30 days
≥2 months	≥60 days
≥3 months	≥90 days
≥6 months	≥180 days
≥9 months	≥270 days
≥12 months	≥360 days

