#### 3.8.5 Safety data cutoff and visit windows for summaries on follow-up set

For safety summaries on the safety set, only data which are within 45 days (5 times the half life of FTY720, 9 days) after the last dose of study drug will be considered.

For safety summaries on the follow-up set, all data (including assessments or events more than 45 days after the last dose of study drug) will be considered.

The visit windows below will be used in summaries on the follow-up set.

- 1) Last assessment on study drug
- 2) Day 1 to 45 after study drug discontinuation

- 3) Month 3 (day 46 to 135) after study drug discontinuation
- 4) Month 6 (day 136 to 270) after study drug discontinuation
- 5) Month 12 (day 271 to 540) after study drug discontinuation

For the visit window 1), last assessment on or before the last dose date will be used. For visit windows 2) to 5), assessments collected during the specified day intervals after the last dose date will be used.

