## 8 Safety evaluation

Safety assessments include adverse events, infections, bradycardia events, laboratory tests, vital signs, ECG, pulmonary function tests (PFTs), ophthalmic examinations, and dermatology assessment.

All safety data will be summarized on the safety set. Some safety data (AEs, vital signs, labs, PFTs, and ophthalmic evaluations) will also be summarized on the follow-up set.

Unless otherwise specified, safety assessments more than 45 days after the study drug discontinuation will not be included in the summaries on the safety set but will be considered in the summaries on the follow-up set. The 45 days rule should be applied as follows:

45 days after the last study drug dose date will be the cutoff for safety data to be included in the summaries.

Adverse events starting/ending before the first dose date will be excluded from the adverse event summaries i.e. only treatment emergent AEs will be summarized by treatment.

Details of the safety data summaries will be provided in the sections below. All safety data will also be presented in the listings.

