## 8.1 Adverse events

## 8.1.1 Adverse event date imputation

To ensure that all reported AEs are summarized, a conservative approach will be taken to impute the AE date when a partial date is available. AE date imputation is based on a comparison of the partial AE start date to the treatment start date (Table 4-1).

- 1. If the AE start date year value is missing, the AE start date will be imputed as the treatment start date.
- 2. If the AE start date year value is less than the treatment start date year value, the AE must have started before treatment. The following imputation rules will apply.
  - a. If the AE month is missing, the AE start date will be imputed as the mid year date (01JulYYYY).
  - b. If the AE month is not missing, the AE start date will be imputed as the mid month date (15MONYYYY).
- 3. If the AE start date year value is greater than the treatment start date year value, the AE must have started after treatment. The following imputation rules will apply.
  - a. If the AE month is missing, the AE start date will be imputed as the year start date (01JanYYYY).
  - b. If the AE month is not missing, the AE start date will be imputed as the month start date (01MONYYYY).
- 4. If the AE start date year value is equal to the treatment start date year value, the month values will be compared as follows.
  - a. If the AE month is missing or the AE month is equal to the treatment start month, the AE start date will be imputed as the date one day after treatment start date.
  - b. If the AE month is less than the treatment start month, the AE start date will be imputed as the mid month date (15MONYYYY).
  - c. If the AE month is greater than the treatment start month, the AE start date will be imputed as the start month date (01MONYYYY).

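### A partial last-dose date is set to its earliest possible value, ahead of a complete dosing-record date and with no floor at first dose

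*SAP*

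**What the plan says.** SAP 3.8.7 names three sources for the last dose date: the study completion form and the study drug discontinuation form (both CMP panel), and the dosing record (DAR panel). CMP has priority: "The last dose date recorded in the CMP panel will be used". For a partial CMP date: "If the last dose date in the CMP panel is partial date, impute the first day for missing day and January for missing month". The dosing record is only a last resort: "If the last dose date in the CMP panel is completely missing, the last dose date recorded on the DAR panel will be used". No lower limit at the first dose date is stated.

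This date then controls several things:
- The safety-set cutoff. SAP 3.8.5 admits "only data which are within 45 days (5 times the half life of FTY720, 9 days) after the last dose of study drug", and SAP 8 repeats it: "45 days after the last study drug dose date will be the cutoff for safety data to be included in the summaries".
- The boundary between the Month 12 and Follow-up windows (SAP 3.8.3.2, Tables 2-1 to 2-5).
- The per-protocol analysis. Time on drug is last dose minus first dose plus 1, and its log is the offset (SAP 4.2.1.2). Only relapses starting on or before the last dose count (SAP 4.2.1.3).
- The MRI sensitivity analyses that exclude end-of-treatment scans more than 45 days after last dose (SAP 4.2.2.1, Table 3-3).

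SAP 3.6 has the same earliest-date rule for the last dosing interval on the DAR, used for exposure: "if the dosing end date is partial date, impute the first day for missing day and January for missing month".

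**The concern.** An incomplete form entry overrides a complete date recorded elsewhere, and the substitute is the earliest date that the entry allows. The error therefore always runs one way: the recorded end of treatment is never too late and usually too early. Since the cutoff, the visit windows and the per-protocol dataset all hang on this date, on-drug observations could be treated as post-treatment or left out of summaries.

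The SAP handles comparable dates differently. SAP 4.2.1.4 floors a partial relapse start at the first dose date when both fall in the same month, and takes a partial relapse end date to the last day of the month, or to the last visit date if that falls in the same month. The last dose date gets neither treatment.

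**Working it through.** **Inputs.** Cutoff: last dose + 45 days (SAP 3.8.5, 8). Lower bound for AEs: the first dose date (SAP 8: "Adverse events starting/ending before the first dose date will be excluded from the adverse event summaries"). Time on drug: last dose − first dose + 1 (SAP 4.2.1.2). The plan's one figure reproduces: 5 × 9-day half-life = 45 days.

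**Size of the shift.**
- Day missing: at most 31 − 1 = 30 days, on average about 15. Since 30 < 45, the imputed cutoff falls at least 15 days after the true last dose, so no on-drug day is lost from the safety set. Only the post-dose tail is cut.
- Day and month missing: at most 364 days (365 in a leap year). With last doses spread evenly over the year, the mean of 0 to 364 is 182 (182.5 in a leap year; a simulation gave 182.5).

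**Worked cases (dates assumed).**

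| Case | First dose | True last dose | Missing | Imputed last dose | Cutoff | Time on drug, imputed (true) | On-drug days past cutoff |
|---|---|---|---|---|---|---|---|
| A | 10 Mar 2015 | 24 Mar 2015 | day | 1 Mar 2015 | 15 Apr 2015 | −8 (15) | 0 of 15 |
| B | 20 May 2015 | 15 Sep 2015 | day, month | 1 Jan 2015 | 15 Feb 2015 | −138 (119) | 119 of 119 |
| C | 5 Dec 2014 | 29 Nov 2015 | day, month | 1 Jan 2015 | 15 Feb 2015 | 28 (360) | 287 of 360 |
| D | 5 Dec 2014 | 29 Nov 2015 | day | 1 Nov 2015 | 16 Dec 2015 | 332 (360) | 0 of 360 |

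In A and B the log of time on drug does not exist. In A, 23 of the 60 days in the safety window (15 on drug + 45) are lost, and in D 28 of 405, all after the last dose. The per-protocol relapse count has no 45-day tail, so in D a relapse starting from 2 to 29 November, while on drug, would be dropped. With a complete and correct DAR date the four durations would be 15, 119, 360 and 360, and nothing would be lost.

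**Per affected patient** (200,000 simulated patients per row; first doses evenly spread over 2013 to 2016):

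| Treatment length | Missing | Last dose before first dose | Mean on-drug days past cutoff (share) |
|---|---|---|---|
| 1–360 days, uniform | day | 4.1% | 0 |
| 1–360 days, uniform | day, month | 50.6% | 98.7 (54.7%) |
| 1–30 days, uniform | day | 49.1% | 0 |
| 1–30 days, uniform | day, month | 95.7% | 13.1 (84.8%) |
| 360 days | day | 0% | 0 |
| 360 days | day, month | 1.5% | 140.1 (38.9%) |

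These rates apply only to patients whose CMP date is partial, not to the trial.

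**The case against.** The strongest reply is that this is a fallback rule with little reach. Much of that stands.

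- A reader might infer that on-treatment safety data are deleted. The documents do not support that in general. The cutoff governs safety-set summaries only. SAEs starting after first dose are kept whatever the last dose date (SAP 8.1.2), C-SSRS data have no cutoff (SAP 8.9), and all safety data are listed (SAP 8). On-drug data leave the safety set only when the month is missing.
- A reader might infer an effect on the primary result. Time in study is the later of the study completion visit and the last dose (SAP 4.1.3), so an early last-dose date is largely harmless there.
- A reader might infer negative exposure. Exposure in SAP 3.6 is built from DAR intervals, which the CMP rule does not feed. The quantity that can go negative through SAP 3.8.7 is per-protocol time on drug.
- A reader might see a contradiction with "To ensure that all reported AEs are summarized, a conservative approach will be taken" (SAP 8.1.1). That sentence concerns AE dates, so it sets no rule for last dose. Nor is the earliest-date approach always anti-conservative: under SAP 3.6 it shortens patient-years and so raises AE rates per 100 patient-years.
- Partial dates should be few, given automatic checks, queries and full verification of primary and safety data (Protocol 8.1 to 8.3). That is fair, although SAP 8.5.3 records a site that did not answer a data query.

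What does not stand is the idea that follow-up tables repair the loss. For labs they carry only summary statistics and changes from baseline (SAP 8.2.3). Notable-abnormality incidence and shift tables, and the PFT counts below 80% and 60% of baseline (SAP 8.5.3), are safety-set only. Nothing in the reply justifies preferring an imputed date to a complete recorded one.

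**Conclusion.** The point holds as a defect in a stated rule with limited reach.

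- **Day missing:** a backward shift of up to 30 days. Part of the 45-day post-dose window is trimmed, late on-drug relapses can leave the per-protocol count, and some early stoppers get a last dose before first dose and cannot enter the per-protocol model.
- **Month also missing:** an average shift of about 182 to 183 days. On-drug non-serious AEs, labs, vital signs and PFTs can leave the safety-set summaries or be labelled as follow-up.

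The per-patient sizes rest on evenly spread first doses and assumed treatment lengths. The trial-level effect is unknown, because neither document says how many CMP dates are partial or whether any lacks the month. That the SAP history dates the rule to 10 September 2018 does not show how many patients it touches.

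**What to change.** In SAP 3.8.7, when the CMP date is partial:
1. Use the DAR end date if it is complete and agrees with the known parts of the CMP date.
2. Otherwise, if only the day is missing, use the last day of the month, capped at the last visit date. This is the SAP 4.2.1.4 convention for relapse end dates.
3. If the month is also unknown, default to neither 1 January nor December. Patients who stop drug stay in the study (Protocol 5.5.10), so a December default capped at the last visit could count months off drug as on drug. Bound the date with dispensing, accountability and visit records, and show the affected per-protocol and safety summaries under the earliest and latest consistent dates.
4. In every case, floor the date at the first dose date.

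In SAP 3.6, floor a partial DAR end date at the start of that dosing interval. Report the number of partial dates by arm, so that the reach can be judged.

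The cost is a few sentences of SAP text, a few lines of code and, if any year-only dates exist, a second run of the affected tables. On-drug time may be slightly overstated for a few patients.

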# 3.9 Pooling of centers

Total 6 countries participate in this study (Argentina, Brazil, Canada, Chile, Mexico and US) with majority of subjects from US. Region will be defined by pooling of centers as follows and will be used in the analysis as a factor.

- Centers from Latin American countries (i.e. Argentina, Brazil, Chile, and Mexico) will be pooled as a region called Latin American region.
- Centers from US/Canada will be pooled according to their geographic location and the number of subjects randomized as follows.
  - 1. Centers from US states of CA, WA, OR, NV, AZ, MT, UT and Canadian western provinces of British Columbia, Alberta, Saskatchewan, and Manitoba will be pooled as a region called West region.
  - 2. Centers from states of TX, CO, NM, KS, OK, MO will be pooled as a region called Southwest region.
  - 3. Centers from states of WI, IA, IL, MI, IN, OH, KY, WV will be pooled as a region called Midwest region.
  - Centers from US states of NJ, PA, MD, DC, DE, VT, NH, MA, CT, NY and Canadian Eastern provinces of Quebec, Ontario and Nova Scotia will be pooled as a region called Northeast region.
  - 5. Centers from states of FL, TN, AL, GA, LA, VA, NC, SC, PR will be pooled as a region called Southeast region.

The pooling of centers is performed so that there will be sufficient number of subjects in each region. If a statistical model stratified by region does not converge due to small number of subjects or small number of events in one or more regions, then regions will be further combined as needed.

# 4 Efficacy evaluation

# 4.1 Primary and key secondary efficacy variables

#### 4.1.1 Primary efficacy variable

The primary efficacy variable is the annualized relapse rate (ARR) which will be analyzed on both the full analysis set (primary analysis) and the per-protocol set (supportive analysis). The ARR can be calculated in two ways:

1. Group level (aggregate ARR)

The ARR of a treatment group is calculated as the sum of the number of confirmed relapses of all subjects in the group divided by the sum of the number of days in study of all subjects in the group and multiplied by 365.25.

The group level ARR is the primary efficacy variable.

#### 2. Subject level

The ARR of an individual subject is calculated as the number of confirmed relapses divided by the number of days in study and multiplied by 365.25. The ARR of a treatment group is the mean of ARRs of all subjects in the group.

#### 4.1.2 Key secondary efficacy variable

Not applicable.

#### 4.1.3 Time in study (years) for aggregate ARR

Time in study is the number of days from the first study drug dose date to the study completion visit date or the last study drug dose date whichever occurs later. It will be calculated as:

Time in study = Max (Study completion visit date, last study drug dose date) – first study drug dose date + 1

Note that the study complete visit date is defined as follows:

- 1. For subjects who completed study drug, or completed the abbreviated schedule of assessments after discontinuing the study drug prematurely, the study completion visit date is the Visit 7/Month 12 visit date.
- For subjects who discontinued study drug prematurely and did not complete the abbreviated schedule of assessments, the study completion visit date is the end of study (EOS) visit date.
   If a subject did not have an EOS visit date, then the last study visit date excluding follow-up visit will be used

The time in study (years) will be calculated as the number of days in study/365.25.

The confirmed relapses within this time period will be counted for each subject and will be used in the ARR computation.

# 4.2 Statistical methodology

#### 4.2.1 Primary analysis

The 2 doses of fingolimod will be tested hierarchically vs. glatiramer acetate in a step-down procedure. For each of the 2 fingolimod doses, the null hypothesis is that there is no difference in the

ARRs between subjects treated with fingolimod and those treated with glatiramer acetate versus the alternative hypothesis that there is a difference between the 2 treatment groups. In order to preserve the Type I experiment-wise error rate, the null hypothesis will be rejected if the observed *p*-value for the between-treatment comparison is less than the significance level as specified in the multiplicity adjustment procedure described later in this section.

 $H_{01}$ :  $\mu_{FTY\,0.5\,mg}$  =  $\mu_{glatiramer\,acetate}$  versus  $H_{A1}$ :  $\mu_{FTY\,0.5\,mg} \neq \mu_{glatiramer\,acetate}$ 

 $H_{02}$ :  $\mu_{FTY 0.25 \text{ mg}} = \mu_{glatiramer acetate}$  versus  $H_{A2}$ :  $\mu_{FTY 0.25 \text{ mg}} \neq \mu_{glatiramer acetate}$ 

No formal hypothesis will be tested between the 2 fingolimod doses because the study is not powered to detect a difference in treatment effect between the 2 fingolimod doses.

The hypotheses will be tested using a negative binomial regression model with log link, using treatment as main effect, using the number of relapses in the previous year before study enrollment, baseline EDSS, and baseline Gd + T1 lesion count and country (or region) as covariates.

In the negative binomial regression model, the response variable is the number of confirmed relapses for each subject. The subject's time in the study (natural log of time in years) is used as an offset variable to obtain the ARR, adjusted for the varying lengths of subject's time in the study (time in years). Study centers will be pooled to country or region (based on geographical proximity and/or known or expected regional differences in medical care) in order to minimize the impact of low enrolling centers/countries on the analysis (such as non-convergence of the analysis model). Details of pooling will be provided in the statistical analysis plan before database lock. The SAS procedure GENMOD (or other software with similar functionality) will be used to conduct the analysis.

The treatment effect of each dose of fingolimod versus glatiramer acetate will be presented as an ARR ratio ( $\mu_{FTY}^{\wedge}/\mu_{GA}^{\wedge}$ ) with corresponding 95% confidence intervals and p values. In addition, the relative reduction in ARR will be presented as "percentage change," calculated as ( $\mu_{FTY}^{\wedge}/\mu_{GA}^{\wedge}$ -1).

The primary analysis will be conducted on the full analysis set. Only confirmed relapses will be counted.

#### 4.2.1.1 Multiplicity adjustment for statistical hypothesis testing

The primary hypotheses tests will be tested using a hierarchical step-down procedure to control the experiment-wise error rate.

This study is designed to compare each of 2 doses of fingolimod to glatiramer acetate based on ARR. There are 2 hypotheses being tested (H01, H02).

Because it is highly likely that the approved dose of fingolimod (0.5 mg) is more efficacious than the lower dose (0.25 mg), the approved dose of fingolimod is initially tested against glatiramer acetate at a 2-sided significance level of 0.05. Only if this initial test H01 is rejected, will the low dose of fingolimod, be tested against glatiramer acetate also at a 2-sided significance level of 0.05.

Different scenarios of the anticipated treatment effect between fingolimod 0.5mg or 0.25mg versus glatiramer acetate have been evaluated based on the available data on fingolimod and the cumulative literature on glatiramer acetate. A 30% treatment benefit of fingolimod 0.5mg over glatiramer acetate could be anticipated on the basis of double-blind, 24-months, placebo-controlled studies of glatiramer acetate (Johnson et al, 2001) and fingolimod [Study CFTY720D2301] alone. However, more recent studies on glatiramer acetate, in a less active population, in a total of over 3000 patients, suggest that the efficacy of glatiramer acetate on ARR and other endpoints is similar to that of IFN beta-1a SC (REGARDS) or IFN beta-1b SC (BEYOND). The observed relapse rates on

Protocol No. CFTY720D2312

with glatiramer acetate (ARR=0.30) is assumed.

Fingolimod 0.25 mg has never been tested in a clinical trial. Based on PK/PD modeling a 14% higher ARR in patients on fingolimod 0.25 mg compared to those on fingolimod 0.5 mg is anticipated. However, the uncertainty of this estimate is substantial. A 95% confidence interval from the PK/PD model for the ARR in patients on fingolimod 0.25 mg ranges from ARR=0.183 to ARR=0.303. For the purpose of this study, an ARR of 0.225 is assumed in patients treated with fingolimod 0.25 mg, which corresponds to an increase in ARR of approximately 15% compared to fingolimod 0.5 mg and a relative treatment effect of 25% compared to glatiramer acetate.

glatiramer acetate were 0.29 in REGARDS and 0.34 in BEYOND, compared to 0.3 (INF beta-1a SC) and 0.33 (INF beta-1b SC), respectively. In Study FTY720D2302, a double-blind 1-year study, fingolimod 0.5 mg was directly compared to IFN beta-1a IM. The ARR (0.21) in patients treated with fingolimod 0.5 mg was reduced by 52% compared to the ARR (0.43) in patients treated with INF beta-1a IM. Overall, the reduction in ARR in patients treated with fingolimod 0.5 mg compared to those treated with glatiramer acetate can be expected in the range of 30% to 50%. For the purpose of this study, a 35% lower ARR in patients treated with fingolimod 0.5 mg (ARR=0.195) compared to those treated

